13.3 EVALUATION OF BEST OVERALL RESPONSE

The best overall response is the best response recorded from the start of the treatment until disease progression/recurrence.

Table 6. Best Overall Response

Target Lesions	Non-Target Lesions	New Lesions	Overall Response
CR	CR	No	CR
CR	PR/SD	No	PR
PR	Non-PD	No	PR
SD	Non-PD	No	SD
PD	Any	Yes or No	PD
Any	PD	Yes or No	PD
Any	Any	Yes	PD

Given the observed pattern of response with immunotherapy medications where some patients develop evidence of progressive disease by RECIST 1.1, with significant increase in size of target lesions and/or new lesions, followed by regression of disease to SD or PR/CR all imaging showing progressive disease by RECIST 1.1, in the absence of significant clinic deterioration of the patient will be confirmed with a repeat CT scan at least 4 weeks from the initial imaging showing progression. Clinically stable patients will continue treatment in the interim before this scan. If progressive disease is confirmed on subsequent imaging, the patient will be defined as having progressive disease and will be taken off of the study. Progressive disease by RECIST 1.1 with clinical deterioration by the patient will be counted as progressive disease, and study treatment will be discontinued.

Determination of clinical deterioration is at the discretion of the treating physician as defined by progression of disease at critical sites requiring urgent intervention (for example cord compression), or development of signs and symptoms of disease progression and/or significant decline in ECOG performance status.

14.0 TISSUE AND BLOOD COLLECTION AND BIOMARKER STUDIES

The following exploratory biomarker analysis will be conducted:

1. To evaluate changes in immune gene expression, immune co-signaling molecule expression by IHC, and immune cell populations over time via paired samples after exposure to combination immunotherapy
2. To evaluate co-signaling molecule expression by IHC and correlate with gene expression by RNAseq as well as the predictive value of co-signaling molecule expression by IHC and the efficacy of the combination selected.
3. Evaluation of immune cell populations and other potential biomarkers (as detailed in section in the peripheral blood at baseline and over time).
4. To evaluate the predictive value of the oral and stool microbiome on efficacy with treatment.

14.1 TISSUE ANALYSIS.

14.4 ORAL RINSE AND STOOL FOR MICROBIOME ANALYSIS

Oral rinse will be collected at the following time points for both arms on the study, to coincide with blood drawing time points:

1. Cycle 1 Day 1 of study therapy prior to infusion of the study therapy
2. Cycle 3 Day 1 of study therapy prior to infusion of the study therapy
3. At the next visit after progression of disease is confirmed (if applicable)

For oral rinse, the patient should pour approximately 10cc of saline into his/her mouth and vigorously swish it against the cheeks for 10 seconds and deliver the solution with a sterile beverage straw into a labeled 15cc polypropylene test tube. Ship the day of collection at ambient temperature overnight.

Coordinator and subject to wear gloves. Saline to be given in a sterile specimen cup and then that cup discarded.

- Have participant ACTIVELY gargle 10ml of sterile saline for 60 seconds.
- Ask participant to swish the saline in the mouth for 5 more seconds and spit oral wash into a new sterile specimen cup.
- Cap the specimen cup and place sample on ice.
- Using moderate pressure, rapidly scrape the tongue 6 times to accumulate a buildup of debris on the sterile, disposable tongue scraper.
- Swirl the tongue scraper in the conical with PBS. Discard tongue scraper.
- Store on ice until transferred to lab for processing.

14.5 FUTURE BIOMEDICAL RESEARCH

With patient consent, the UPMC Hillman Cancer Center will conduct future biomedical research on blood and tumor tissue specimens collected during this clinical trial. This research may include but is not limited to genetic analyses (DNA), gene expression profiling (RNA), proteomics, metabolomics (serum, plasma) and/or the

measurement of other analytes. Such research is for biomarker testing to address emergent questions not described elsewhere in the protocol (as part of the main trial). The objective of collecting specimens for future biomedical research is to explore and identify biomarkers that inform the scientific understanding of diseases and/or their therapeutic treatments.

Estimate the disease control rate (DCR), progression-free survival (PFS), overall survival (OS) and safety of treatment determined by gene expression of LAG3 and CTLA4 per OmniSeq Immune Report card for R/M HNSCC patients who have progressed on prior immunotherapy. The analysis of DCR is similar to that of objective response. PFS and OS will be analyzed by means of proportional hazards (Cox) regression models including treatment and OmniSeq response score as covariates. Safety, represented by serious adverse events at least possibly related to treatment, will be analyzed in a similar fashion to the primary endpoint, where each participant will be scored as experiencing or not experiencing at least one such events. All point estimates will be accompanied by 95% credible or confidence intervals. Adverse events will also be tabulated by type, grade and relatedness to treatment.

15.2.3 SECONDARY OBJECTIVE 2

Estimate the probability of objective response, DCR, PFS, OS and safety of treatment that is randomly assigned instead of determined by gene expression. This will be compared in an exploratory fashion to the objective response of those patients with treatment determined by gene expression. The probability of objective response and DCR will be estimated by logistic regression with treatment, OmniSeq response score and treatment assignment modality (randomized versus OmniSeq) as covariates. PFS and OS will be estimated by proportional hazards (Cox) models. All estimates of odds and hazard ratios will have 95% confidence intervals.

15.2.4 SECONDARY OBJECTIVE 3

Estimate the probability of objective response, DC, PFS, OS and safety of treatment determined by gene expression of LAG3 and CTLA4 per OmniSeq Immune Report card for R/M HNSCC patients who have progressed on trial treatment and undergo a second biopsy and second treatment determined by a second gene expression analysis of LAG3 and CTLA4. The analysis is similar to those in the above aims. It is possible the numbers of participants in this category will not support these analyses, in which case descriptive statistics will be presented.

15.2.5 BIOMARKER STUDIES

15.2.5.1 IMMUNE EXPRESSION

Evaluate immune gene expression, immune co-signaling molecule expression by IHC, and immune cell populations over time via paired samples after exposure to combination immunotherapy. Linear mixed models will be used to characterize the changes in LAG3 and CTLA4 over time, in addition to other markers of interest.

15.2.5.2 CO-SIGNALING MOLECULE AND GENE EXPRESSION

Evaluate co-signaling molecule expression by IHC and correlate with gene expression by RNA-Seq as well as the predictive value of co-signaling molecule expression by IHC and the efficacy of the combination selected. The analysis plan is the same as for immune expression.

15.2.5.3 PERIPHERAL BLOOD ANALYSIS

Evaluate immune cell populations and other potential biomarkers (as per section 14.0) in the peripheral blood at baseline and over time. The analysis plan is the same as for immune expression.

15.2.5.4 MICROBIOME ANALYSIS

Evaluate oral and stool microbiome and correlate the baseline distribution and the change over time with efficacy. The analysis plan is the same as for immune expression.

15.3 MONITORING RULES

15.3.1 MONITORING RULE FOR LACK OF EFFICACY

Pausing rule: The parameters in the above model will be estimated by means of Markov Chain Monte Carlo after every ten patients. If, at any of these analyses,

$$\Pr(\Pr[\pi|\text{Data and Prior}] < 0.10) > 0.75,$$

Accrual to the trial will be paused and the protocol potentially amended. This is summarized in Table 8.

# Patients	Pause if #OR \leq
10	.
20	1
30	2

Table 8. Pausing Rule in terms of number of objective responses

15.3.2 MONITORING RULE FOR EXCESS TOXICITY

Pausing rule: Adverse events sufficient to warrant discontinuation of treatment (Section 12.3) will be monitored in a similar fashion. If, where π indicates the probability of the specified adverse events, at any of these analyses,

$$\Pr(\Pr[\pi|\text{Data and Prior}] > 0.20) > 0.75,$$

Accrual to the trial will be paused and the protocol potentially amended. This is summarized in Table 9.

# Patients	Pause if #Tox \geq
10	3
20	5
30	7

Table 9. Pausing Rule in terms of number of patients with adverse events sufficient to warrant discontinuation of their treatment

15.4 JUSTIFICATION OF DESIGN

This trial uses a Bayesian design and fixes the sample size at 40. It is assumed that under standard of care, the probability of objective response in this patient population is ≤ 0.10 . The combination of nivolumab plus the appropriate inhibitor will be of interest if the proportion of patients experiencing objective response increases to 0.20 or more.

To characterize the operating characteristics of the proposed trials, three sets of simulations were run. One hundred trials were simulated in each set, including evaluation of the pausing rule every 10 patients. In all simulations, it was assumed that an average of 43% of patients would exhibit the favorable OmniSeq response score (as in Morrison, et al), but the actual number was allowed to vary per simulated trial. It was also assumed that on average, half of the patients would have increased LAG3 expression, compared to CTLA4. The assumed probabilities of objective response for the four patient categories are displayed in Table 10.

Simulation	Unfavorable Response Score		Favorable Response Score		All
	Anti-CTLA4	Anti-LAG3	Anti-CTLA4	Anti-LAG3	
1	0.10	0.10	0.30	0.30	0.186
2	0.10	0.10	0.10	0.10	0.100
3	0.20	0.20	0.30	0.30	0.243

Table 10. Assumed probabilities of objective response in the simulations.

In the first simulation set, it was assumed that patients have the unfavorable response score would have a probability of objective response of 0.10 and patients in the favorable response score category would have a probability of objective response of 0.30. In the second set of simulations, it was assumed the probability of objective response in both inflammatory categories was unacceptably low, 0.10. The third simulation assumed higher probabilities of objective response.

In Table 10, it is seen that 11% of trials in Simulation 1 and 5% in Simulation 3, where it is desirable the trials all 40 patients, stop early, while 66% of trials in Simulation 2, where early stopping is desirable, stop early.

Simulation	Stopped Early at n=			
	10	20	30	40
1	0	0.1	0.01	0.89
2	0	0.56	0.1	0.34
3	0	0.04	0.01	0.95

Table 11. Proportions of trials stopping at n=10, 20 or 30 or accruing all 40 patients.

The estimates of π in Tables 11 and 12 agree reasonably well with the true overall probability of objective response in Table. Some variation is due to variability in the numbers of patients with a favorable response score, which had an average of 43%, but was allowed to vary from trial to trial.

Simulation	Median estimated P(OR)	Median 95% Credible Interval
1	0.192	(0.090,0.318)
2	0.095	(0.028,0.195)
3	0.244	(0.129,0.379)

Table 12. Observed estimates of π (probability of objective response overall) in trials accruing 40 patients. Note that these will tend to be biased upwards from the true values in Table 7, which is expected.

Simulation	Median estimated P(OR)	Median 95% Credible Interval
1	0.174	(0.077,0.295)
2	0.045	(0.001,0.159)
3	0.224	(0.116,0.355)

Table 13. Observed estimates of π (probability of objective response overall) at end of trial.

The estimates of π_{jk} and 95% in Tables 13 and 14 are biased slightly upwards when the probability of response in the unfavorable response score is 0.10, but overall these estimates are as expected, given that the numbers in some categories can be quite low.

Simulation	Unfavorable Response Score		Favorable Response Score	
	Anti-CTLA4	Anti-LAG3	Anti-CTLA4	Anti-LAG3
1	0.147 (0.021,0.359)	0.148 (0.020,0.362)	0.293 (0.087,0.593)	0.305 (0.091,0.617)
2	0.114 (0.015,0.304)	0.122 (0.015,0.337)	0.154 (0.023,0.402)	0.198 (0.041,0.480)
3	0.226 (0.062,0.478)	0.240 (0.067,0.489)	0.299 (0.078,0.615)	0.318 (0.089,0.618)

Table 14. Median estimates of π_{jk} and 95% credible intervals in trials accruing 40 patients. Note that these will tend to be biased upwards from the true values in Table 2, which is expected.

Simulation	Unfavorable Response Score		Favorable Response Score	
	Anti-CTLA4	Anti-LAG3	Anti-CTLA4	Anti-LAG3
1	0.145 (0.020,0.358)	0.142 (0.020,0.364)	0.276 (0.069,0.586)	0.302 (0.079,0.615)
2	0.106 (0.003,0.346)	0.106 (0.003,0.369)	0.145 (0.004,0.446)	0.143 (0.004,0.448)
3	0.226 (0.062,0.478)	0.240 (0.066,0.489)	0.299 (0.078,0.615)	0.318 (0.088,0.618)

Table 15. Median estimates of π_{jk} and 95% credible intervals at end of trial.

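### The Simulation 2 early-stopping figures in section 15.4 do not follow from the plan's own pausing rule (about 49%, not 66%), and the accuracy wording contradicts Tables 13 and 14

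*Combined protocol and SAP*

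**What the plan says.** Section 15.4 states the design: "This trial uses a Bayesian design and fixes the sample size at 40". The reference rates are 0.10 or less under standard of care and 0.20 or more as the level of interest. On the simulations it says "One hundred trials were simulated in each set, including evaluation of the pausing rule every 10 patients". In Simulation 2 "it was assumed the probability of objective response in both inflammatory categories was unacceptably low, 0.10"; Table 10 gives 0.10 in all four cells.

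The reported results relevant here are:

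- **Table 11, Simulation 2:** 0, 0.56, 0.10 and 0.34 of trials end at n=10, 20, 30 and 40. The text sums the early stops to 66%.
- **Overall response rate:** the estimates are said to "agree reasonably well with the true overall probability of objective response". The sentence cites Tables 11 and 12, but Table 11 holds stopping proportions. The estimates are in Tables 12 (trials reaching 40) and 13 (end of trial).
- **Cell estimates:** they "are biased slightly upwards when the probability of response in the unfavorable response score is 0.10", and are otherwise called as expected given small cells. The sentence cites Tables 13 and 14; the cell estimates are in Tables 14 and 15.
- **Table 12 note:** "Note that these will tend to be biased upwards from the true values in Table 7, which is expected". Table 7 is the treatment-assignment table; the true rates are in Table 10.

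Section 15.3.1, Table 8 gives the rule: no pause at n=10, pause at 1 or fewer responses at n=20, and at 2 or fewer at n=30.

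**The concern.** Estimating the response probability is the primary objective, and section 15.4 is the only support the plan gives for how well 40 patients can do that. Simulation 2 alone shows what happens when the treatment does not work. Its early-stopping figure is what a reader would use to judge protection against continuing an ineffective strategy. If the figure is too high, that protection is overstated. If the text calls the estimates accurate where the tables show large errors, readers are misled about a trial that stops early and about the cell-level results.

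**Working it through.** **Inputs.** True rates from Table 10; limits from Table 8; stated proportions from Table 11; 100 trials per set; 43% favourable score on average. Table 8 depends only on total responses. With patients independent, the total is binomial with the overall rate.

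**1. Reproduce what reproduces.** Table 10 overall rates: 0.57×0.10 + 0.43×0.30 = 0.186; 0.100; 0.57×0.20 + 0.43×0.30 = 0.243. All match. Table 8 follows from P(Beta(y, n−y) < 0.10) > 0.75:

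- n=10, y=1: 0.613 (no pause)
- n=20: y=1 gives 0.865, y=2 gives 0.580
- n=30: y=2 gives 0.801, y=3 gives 0.565

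**2. Stopping probabilities.** Stop at n=20: P(X20 ≤ 1). Stop at n=30: P(X20 = 2) × P(no response in the next 10). For p=0.10:

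- n=20: 0.1216 + 0.2702 = 0.392
- n=30: 0.2852 × 0.3487 = 0.099
- total 0.491; reach 40: 0.509

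| Simulation | n=20 exact / stated | Total exact / stated |
|---|---|---|
| 1 | 9.1% / 10% | 11.2% / 11% |
| 2 | 39.2% / 56% | 49.1% / 66% |
| 3 | 2.8% / 4% | 3.3% / 5% |

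**3. Could 100 replicates explain Simulation 2?** At n=20 the standard error is √(0.392×0.608/100) = 0.049, so the gap is (0.56 − 0.392)/0.049 = 3.4 SE. The exact probability of 56 or more is 0.0005; of 66 or more stops in total, also 0.0005. The two overlap and are not independent evidence. The n=30 entry fits (9.9% against 10%). Pausing at 2 or fewer at n=20 would give 67.7%, so that does not produce 56% either.

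**4. Stated estimates against the truth (estimate/truth − 1).**

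| Table | Simulation 1 | Simulation 2 | Simulation 3 |
|---|---|---|---|
| 12, overall | +3.2% | −5.0% | +0.4% |
| 13, overall | −6.5% | −55.0% | −7.8% |

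Table 14 cells with truth 0.10: Simulation 1 unfavourable 0.147 and 0.148 (+47%, +48%); Simulation 2 0.114, 0.122, 0.154 and 0.198 (+14%, +22%, +54%, +98%).

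**5. How much of 0.045 is expected?** For p=0.10 the crude end-of-trial proportion is at most 1/20 in 39.2% of trials, at most 2/30 in 49.1%, and at most 3/40 in 55.3%. The median is therefore 0.075, or −25%. A median of 0.05 or less needs about 50 or more of 100 trials stopping at n=20, which has probability 0.018. So 0.045 is consistent with Table 11's 56% but not with Table 8.

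**6. The 0.198 cell.** Rebuilding the section 15.2.1 model gives medians of about 0.10 to 0.13 in all four Simulation 2 cells among trials reaching 40, depending on the posterior summary. With about 34 such trials the Monte Carlo SE of the median is about 0.018 to 0.02. Then (0.198 − 0.127)/0.018 = 3.9 and (0.198 − 0.104)/0.02 = 4.7.

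**7. Estimates after a pause.** If the trial ends there, the mean crude rate at p=0.10 is (0.2702×1/20 + 0.0994×2/30)/0.491 = 0.041; the same formula at p=0.186 gives 0.046.

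**The case against.** Most of the stated results are sound. Five of the six overall estimates in Tables 12 and 13 lie within 8% of the truth. The −55% comes under the agreement sentence only after its references are read as Tables 12 and 13, though no other reading gives the sentence two tables of estimates. Some downward shift at end of trial is what any futility rule produces. The plan discloses upward cell bias and blames small cells, and relative errors on a base of 0.10 look large: 0.047 in absolute terms, inside an interval of 0.021 to 0.359. All of this stands, and it limits the point. It does not rescue the Table 11 row or the 0.198 cell, because the recomputation uses equally small cells.

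The simulations may have paused on the full hierarchical model rather than on Table 8. A rebuild with looks at n=20 and 30 gave 38% at n=20 and about 41% in total. Adding the n=10 look gave about 36% at n=10, 13% at n=20 and 50% in total. Neither yields 56% or 66%, and Table 11 shows no stops at n=10.

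A reader might also infer that Table 12's 0.095 proves an error, since trials reaching 40 have at least 3 responses and a crude median of 5/40 = 0.125. That is too strong: 0.095 corresponds to about 4/40, and a median that low among 34 trials has probability about 0.04 to 0.08. Nor do the documents support saying that a paused trial must report 4 to 5%. Those are crude rates, whereas the plan reports a posterior with the response count floored at 1, and section 15.3.1 provides for a pause and possible amendment, not termination.

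**Conclusion.** The point holds for Simulation 2 and for two sentences of text. Early stopping under the null is overstated: about 49% rather than 66%, with 50.9% rather than 34% reaching 40 patients. This rests on Table 8 being the rule simulated, independent patients, and a true rate of 0.10. The sentence on overall response is contradicted by 0.045 against 0.100, of which a fall to about 0.075 is ordinary early-stopping bias. The word describing the cell bias as slight is contradicted by 0.147 to 0.198 against 0.10. The cell recomputation depends on implementation, so a range is given; 0.198 lies about 4 SE or more outside it.

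A reader might infer that the simulations as a whole, the pausing limits or the primary analysis are invalid. The documents do not support that: Table 8 and Simulation 1's stopping row reproduce, Simulation 3 is within noise, and Tables 12 to 15 drive no conduct rule. The cause of the Simulation 2 discrepancy cannot be determined from the documents. The figures should be corrected because they are stated operating characteristics of the only null scenario.

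**What to change.** Re-run Tables 11 to 15 with the final model and the Table 8 limits, using enough replicates to make Monte Carlo error small, and state the number. Restate the Simulation 2 early-stopping probability (about 49% under Table 8). Name the posterior summary tabulated. Correct the table references in the text and notes of section 15.4. Replace the agreement wording and the description of the cell bias with the actual biases by scenario. Add a sentence that estimates from a trial ending at a pause are biased downward. A bias-adjusted estimator is optional and not part of this correction.

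The cost is some computing time, replacement text and tables, and a less favourable stated probability of stopping early when the treatment does not work.

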16.0 STUDY MANAGEMENT, AGREEMENT AND ETHICAL CONSIDERATIONS

16.1 STUDY MANAGEMENT

If a protocol amendment requires a change to the Written Informed Consent Form the participating IRB must be notified. The sponsor is responsible for the distribution of these documents to the participating IRB and study staff.

16.2 STUDY AGREEMENT

The Sponsor-Investigator must comply with all the terms, conditions, and obligations of the Clinical Study Agreement for this study. The Sponsor-Investigator reserves the right to conduct interim analyses during the study

16.3 ETHICAL CONSIDERATIONS

16.3.1 ETHICS REVIEW

The final study protocol, including the final version of the Written Informed Consent Form, must be approved or given a favorable opinion in writing by an IRB.

The Sponsor-Investigator is responsible for informing the IRB of any amendment to the protocol in accordance with local requirements. In addition, the IRB must approve all advertising used to recruit subjects for the study. The protocol must be re-approved by the IRB annually, as local regulations require. The Sponsor-Investigator is also responsible for providing the IRB with reports of any serious adverse drug reactions from any other study conducted with the investigational product.

16.3.2 ETHICAL CONDUCT OF THE STUDY

The study will be performed in accordance with ethical principles that have their origin in the Declaration of Helsinki and are consistent with Good Clinical Practice, and applicable regulatory requirements.

18.0 APPENDICES

APPENDIX I: ECOG PERFORMANCE STATUS SCALE

Grade	ECOG
0	Fully active, able to carry on all pre-disease performance without restriction.
1	Restricted in physically strenuous activity but ambulatory and able to carry out work of a light or sedentary nature, e.g., light house work, office work.
2	Ambulatory and capable of all self-care but unable to carry out any work activities. Up and about more than 50% of waking hours.
3	Capable of only limited self-care, confined to bed or chair more than 50% of waking hours.
4	Completely disabled. Cannot carry on any self-care. Totally confined to bed or chair.
5	Dead

